9.4 Data sources

THIN

Established in 2002, THIN now collects data from close to 500 practices, covering about 5% of the general population, with more than 65 million patient-years of experience (CSD Medical Research, 2012). Eleven million individual patients are represented in the data; of those, approximately one-third are active at any one time. THIN records information on all services provided by the PCP, and information on specialist visits and hospitalizations are routinely forwarded to the PCP, who enters that information into the medical record. The population included in THIN is representative of the UK as a whole in terms of age, sex and geographic distribution (Blak et al. 2011; Bourke, Dattani, and Robinson 2004). THIN has been extensively validated for use in pharmacoepidemiology (Lewis et al. 2007).

The Read classification is used to code specific diagnoses as reasons for each consultation (Stuart-Buttle et al. 1996), and a drug dictionary based on data from the MULTILEX classification is used to record prescriptions (FDB (First Databank) n.d.).

9.5 Study size

Study 19330 (unpublished data) conducted in UK identified 8,629 initiators of apixaban and 12,353 initiators of rivaroxaban among patients with NVAf from 2011 through 2016 within the THIN database. A study conducted in UK between 1 December 2012 and 31 October 2014 using CPRD, reported 10,218 naïve users of warfarin (Johnson et al. 2016). With an additional year up to 2017, the expected numbers of Rivaroxaban, Apixaban and Warfarin users will be greater than numbers reported above. Thus, assuming the study will include at least 10,000 initiators of each study drug and annual rates of intracranial hemorrhage, ischemic stroke, and all-cause mortality of 1%, 2%, and 4%, we expect the study to identify at least a total of 900, 1800, and 3600 events respectively. In case only 50% of initiators continue drug use at index date (i.e. current users at index date), we should be able to detect, with a statistical power greater than 80%, odds ratios of 1.5 associated to current use of each study drugs for intracranial haemorrhage, odds ratios of 1.3 for ischemic stroke, and odds ratios of 1.2 for all-cause mortality.

Regarding the daily dose analyses, power calculation will depend largely on the percentage of individuals we found in each daily dose category. For instance in, if we assume that 30% of current users of apixaban will use a reduced dose (2.5mg Bid), half of them appropriately, for the comparison between “appropriate” and “inappropriate” reduced dose of apixaban we would be able to detect odds ratios of 3.5 when exploring intracranial hemorrhage, odds ratios of 2.4 for ischemic stroke, or odds ratios 1.8 for all-cause death. On the other hand for the comparison between “inappropriate” reduced dose of apixaban versus warfarin current use, if the assumptions described above hold, we should be able to detect with a power of at least 80% odds ratios of 2.3, 1.8, and 1.6 for ICH, IS, and all-cause mortality respectively. Note that all these calculations have assumed a two-sided type I error of 5%.

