Bayer has recently conducted a retrospective cohort study on prescription patterns of NOACs in NVAF patients in UK general practice using a combination of the THIN and CPRD databases. Amongst patients without an apparent indication for dose reduction, the reduced dose was prescribed in approximately 30% of patients receiving apixaban and 10% of patients receiving rivaroxaban in the new-users of both agents (Study 19330, unpublished data). We therefore hypothesize that in the UK, the higher than expected rates of reduced dose apixaban use as compared to the Phase III trials will exhibit higher rates of stroke and systemic embolism versus warfarin than rivaroxaban, which appears to be prescribed at the reduced dose less frequently. Also, patients with renal impairment receiving standard dose are at increased risk of bleeding. Although, warfarin use has certainly decreased in the recent years, this drug remains the main oral anticoagulant used in the UK. It has also been the active comparator of choice in most clinical trials of NOAC (O'Dell et al.) and in our opinion constitutes an ideal reference drug for these analyses. Both the standard and the reduced dose of NOACs have been compared to warfarin in clinical trials and shown to be as safe and effective as warfarin. Warfarin itself does not have dose-reduction requirements however the dose needs to be adjusted to maintain INR between 2.0-3.0. Rivaroxaban and apixaban are most widely used NOACs in the UK whereas the use of dabigatran is low and declining since 2014 (Study 19330, unpublished data). Also, the appropriate and inappropriate use of dabigatran is difficult to estimate due to a multiple criterion in the label for dose reduction which is difficult to assess using secondary data sources. Risk of major bleeding especially GI bleeding for NOACs is extensively studied, and our research question is to study the effect of under-dosing on the risk of stroke (effectiveness outcome). However, to also study the other side of the balance which is bleeding, we included ICH because it is an event comparable to stroke in terms severity. GI bleeding is an acute event, usually followed by complete recovery in vast majority of patients. In terms of the balanced outcomes, it is important to take account of the severity of the disease events prevented and caused by the intervention, and not just the frequencies of the events. Thus GI bleeds, which are sometimes severe, are acute events usually followed by recovery without sequelae, while strokes and ICH can leave residual physical and/or cognitive impairments in those who survive, and may require complex and lifelong interventions. Therefore, GI Bleeding is not included as an outcome in this study.

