9.2.2 Study time frame

The study period extends from 1st January 2012 up to last available database extraction (at time of writing, December 2017). Rivaroxaban was first marketed in 2008 in the UK, whereas apixaban was introduced in 2011. By choosing this study period we ensure that all three study drugs were available throughout the study.

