9.7 Data Analysis

We will first describe the three cohorts according baseline characteristics, use of medications, comorbidities and healthcare utilization services (see variables in section 9.3). This analysis will be based on descriptive statistics: frequencies and percentages will be calculated to the variables of interests, continuous and count variables will be described using mean (\pm standard deviation), proportions, median (quartiles) and minimum and maximum values. 95% confidence intervals will be computed for descriptive variables.

Two independent follow-ups will be performed, one for each analysis. **Safety and effectiveness:** In this follow-up members of all three study cohorts will be followed from the day after start date up until the earliest of: a) first occurrence of Intracranial hemorrhage (intracerebral hemorrhage, subarachnoid hemorrhage, subdural and epidural hematoma), b) an ischemic event (Ischaemic Stroke /Systemic Embolism), c) Myocardial Infarction, d) death, and e) end of study period. **All-cause Mortality:** the follow-up of members of all three study cohorts will be followed from the day after start date up until the earliest of: a) date of death, and b) end of study period. The end of study period is defined as end of last data collection in each practice.

We will then analyze safety, effectiveness, and all-cause mortality associated to use of the study drugs in three independent nested-case control analyses. These three analyses will include all cases identified in each follow-up (respectively: intracranial hemorrhage events, ischemic events, and deaths) and an analysis-specific group of controls. These control groups will comprise a random sample of members of all three cohorts, frequency-matched by age, sex and calendar year to each set of cases ([Walker 1991](#)). Briefly, each cohort member is assigned a random date within the study period. We will consider “eligible controls” all those individuals who are being followed at the time of the random date (e.g. random date included between their start of follow-up and end of follow-up). This process (similar to incidence density sampling) ensures that the likelihood of being selected as control is proportional to the amount of person-time contributed by each patient: as an example a person who contributes all the time included between beginning of study period and end of study period has a 100% likelihood of being an eligible control. Then we will sample “eligible

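### Section 9.5's minimum event counts need an unstated 3.0-year mean follow-up with nobody leaving, and its overall power statement names neither comparator nor control ratio, so power against warfarin is not given

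*Protocol*

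**What the plan says.** All figures come from Protocol section 9.5 unless noted.

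- **Size and rates.** The calculation starts by "assuming the study will include at least 10,000 initiators of each study drug", with annual rates of 1% (ICH), 2% (ischaemic stroke) and 4% (all-cause death).
- **Events.** From this, "we expect the study to identify at least a total of 900, 1800, and 3600 events respectively". No follow-up time is given.
- **Overall power.** With 50% of initiators still current users at the index date, power above 80% is stated for "odds ratios of 1.5 associated to current use of each study drugs for intracranial haemorrhage", and for odds ratios of 1.3 (stroke) and 1.2 (death). The sentence names no comparator and no number of controls per case.
- **Dose-group power.** Detectable odds ratios are 3.5/2.4/1.8 for appropriate versus inappropriate reduced-dose apixaban, and 2.3/1.8/1.6 for inappropriate reduced-dose apixaban versus warfarin current use. Here the comparators are named.
- **Window.** Section 9.2.2 runs from 1 January 2012 to the last available extraction, December 2017 at the time of writing.
- **Exits.** In section 9.7, patients in the safety and effectiveness analyses are "followed from the day after start date up until the earliest of: a) first occurrence of Intracranial hemorrhage", an ischaemic event, MI, death or the end of the study period.
- **Reference.** Section 8.1 sets every primary objective against warfarin. Section 9.7 makes warfarin current use the reference for the dose categories and non-use the reference for the duration analyses.

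**The concern.** The event counts are offered as a minimum but seem to rest on the most favourable follow-up that even entry into the stated window can give. Every power figure in the section is built on those counts.

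The only power statement for a drug as a whole leaves open what the drug is compared with. Because the primary objectives are all against warfarin, a reader will probably take it as power for that contrast. If the real power for NOAC versus warfarin is lower, a null result could be read as evidence of no difference when the study was too small to show one.

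**Working it through.** **1. Reproducing the event counts.** Initiators: 3 × 10,000 = 30,000.

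- Events per year: 30,000 × 0.01 = 300; × 0.02 = 600; × 0.04 = 1200.
- Implied mean follow-up: 900/300 = 1800/600 = 3600/1200 = 3.0 years.

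Even entry over 6 years with no exits gives a mean of 6/2 = 3.0 years, the same value.

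**2. Follow-up with exits.** With even entry over 6 years and a constant exit rate h, the mean is 1/h − (1 − e^(−6h))/(6h²).

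- Safety and effectiveness: h = 0.01 + 0.02 + 0.04 = 0.07. MI also ends follow-up but has no stated rate, so it is left out. Mean = 14.286 − 0.34295/0.0294 = 2.62 years.
- Mortality: h = 0.04. Mean = 25 − 0.21337/0.0096 = 2.77 years.
- If death alone (h = 0.04) is used for ICH and stroke as well, the counts are 832 and 1664.

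As an assumption, let NOAC entry rise linearly from zero and warfarin entry fall linearly to zero, in line with the trends described in sections 7 and 9.5. Means at h = 0.07 are 1.81 (rising) and 3.43 (falling), so (2 × 1.8065 + 3.4348)/3 = 2.349 years. At h = 0.04, (2 × 1.8855 + 3.6619)/3 = 2.478 years.

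| Entry pattern | ICH | Stroke | Death |
|---|---|---|---|
| Stated | 900 | 1800 | 3600 |
| Even entry, with exits | 786 | 1572 | 3329 |
| NOACs rising, warfarin falling, with exits | 705 | 1410 | 2973 |

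**3. Power method.** Compare exposure in n cases and m controls, two-sided 5%. With p0 the exposure share in controls, p1 = OR·p0/(1 + p0(OR − 1)) and p̄ the pooled share:

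power = Φ{[|p1 − p0| − 1.96·√(p̄(1 − p̄)(1/n + 1/m))] / √(p1(1 − p1)/n + p0(1 − p0)/m)}.

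With 50% current users, each drug is 1/6 of the sample and no current use is 1/2.

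**4. Inferring the control ratio.**

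| Contrast | Stated | 1:1 | 2:1 | 4:1 |
|---|---|---|---|---|
| Appropriate vs inappropriate reduced apixaban (cases = events/6 × 0.30, p0 = 0.5) | 3.5/2.4/1.8 | 3.54/2.37/1.82 | 2.95/2.10/1.68 | 2.66/1.96/1.60 |
| Inappropriate reduced apixaban vs warfarin (cases = events/6 × 1.15, p0 = 0.15/1.15) | 2.3/1.8/1.6 | 2.20/1.78/1.52 | 1.98/1.65/1.43 | 1.86/1.57/1.39 |

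Only 1:1 comes close to both rows.

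**5. Power for odds ratios 1.5/1.3/1.2.**

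| Comparator | Events | 1:1 | 4:1 |
|---|---|---|---|
| All others (p0 = 1/6, all cases) | stated | 93/86/84% | 99/97/96% |
| No current use (p0 = 1/4, 2/3 of cases) | stated | 89/82/80% | 98/95/94% |
| Warfarin current use (p0 = 1/2, 1/3 of cases) | stated | 69/62/61% | 88/82/81% |
| Warfarin current use | 786/1572/3329 | 63/56/57% | 83/76/77% |

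For example, ICH against warfarin at 1:1: n = m = 300, p1 = 0.6, p̄ = 0.55, so Φ[(0.1 − 1.96 × 0.04062)/0.04042] = Φ(0.50) = 69%.

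Odds ratios detectable with 80% power against warfarin at 1:1 are 1.59/1.38/1.26 with the stated counts and 1.64/1.42/1.27 with 786/1572/3329.

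**The case against.** **The power sentence may not be about warfarin.** It speaks of current use of each study drug, and warfarin is a study drug, so non-use is the more natural comparator. On that reading and at 1:1 the stated figures reproduce, with death at 79.8% the only marginal one. A reader might infer that the claim of more than 80% power is false. The protocol does not support that: no comparator or ratio is given, and at 4:1 the claim holds against warfarin too with the stated counts. This stands. What remains is that power for the overall NOAC-versus-warfarin contrast is not given.

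**The control ratio can be left to the SAP.** This is fair, and its absence alone would not be a finding. But section 9.5 states power figures that cannot be interpreted without it.

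**The counts could still be reached.** Section 9.5 assumes at least 10,000 per drug, an earlier study found 12,353 rivaroxaban initiators through 2016, and the extraction date is open. To restore 900 and 1800 events, about 10,000 × 3.0/2.62 ≈ 11,450 initiators per drug would be needed with even entry, or 10,000 × 3.0/2.349 ≈ 12,770 with the mixed pattern. That is possible, so 900/1800/3600 is not an absolute ceiling. But section 9.5 reckons with 10,000 and the year 2017. Apixaban had 8,629 initiators through 2016. If 2017 brings it to 10,000, those 1,371 add at most one year each by December 2017, and the rest would have to average at least (30,000 − 1,371)/8,629 = 3.3 years for apixaban to average 3.0.

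**Two stronger readings fail.**

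- Rising entry for all three drugs would cut the counts much further, but the protocol describes warfarin use as declining.
- The 30% reduced-dose share in section 9.5 has a different denominator from the 30% in section 7. However, section 9.5 presents it as an illustration, and it is conservative for apixaban. It is not an error, and neither is the lack of a separate rivaroxaban example.

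**Practical effect.** The study uses every case found and reports confidence intervals, so imprecision will be visible. That limits the harm but does not correct the stated figures.

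**Conclusion.** The point holds in two parts.

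- **Event counts.** They depend on an unstated 3.0-year mean that leaves no room for the protocol's own exits. With 10,000 initiators per drug and a December 2017 cut, the shortfall under even entry is about 13% for ICH and stroke (786/900, 1572/1800) and 8% for death (3329/3600). Under the assumed mixed entry pattern it is about 22% and 17%. Calling the counts minima is therefore unsupported. They are not impossible, since more initiators or a later extraction could make up the difference. The first calculation rests on constant rates and even entry, the second on linear trends.
- **Power.** The statement for odds ratios 1.5/1.3/1.2 is not shown to be wrong as written, but it does not establish power for the primary comparison. Against warfarin current use, power with the stated counts runs from 61–69% at 1:1 to 81–88% at 4:1. With 786/1572/3329 events, even 4:1 leaves stroke and death below 80%. The 1:1 ratio is an inference from the neighbouring figures.

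**What to change.** Rewrite section 9.5 as follows:

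1. State expected person-years per drug, using the start-date distribution from Study 19330 where it covers the drug, a stated assumption for warfarin, a stated extraction date, and the exits in section 9.7. Derive the event counts from these and drop the minimum wording.
2. Name the comparator for every odds ratio and state the control:case ratio used.
3. Give detectable odds ratios for each NOAC against warfarin current use with the corrected counts, separately from any figures against non-use.

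The cost is one rewritten section and, probably, less favourable figures. No new patients are needed. If more than one control per case is chosen to recover power, the extra cost is dose-history review for the added controls, which section 9.1 describes as not fully automated.

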9.6 Data management

For each study project, all material including: study protocol, copy of Scientific Review Committee approval, algorithms and data collections, datasets, STATA programs, results from validation exercises and questionnaires, final STATA programs, and final report and publications are kept in one folder cross-shared by the CEIFE team. Monthly back-ups are performed and kept in a secure location, and all material is kept for a minimum of 10 years.

As a standard process, one researcher prepares the list of codes, test the computer algorithms to be used and runs statistical analysis after agreement on all phases of analyses with the rest of the team. As one measure of quality control, another researcher independently performs several checks in reviewing commands and analyses performed in order to minimize data errors.

9.7 Data Analysis

We will first describe the three cohorts according baseline characteristics, use of medications, comorbidities and healthcare utilization services (see variables in section 9.3). This analysis will be based on descriptive statistics: frequencies and percentages will be calculated to the variables of interests, continuous and count variables will be described using mean (\pm standard deviation), proportions, median (quartiles) and minimum and maximum values. 95% confidence intervals will be computed for descriptive variables.

Two independent follow-ups will be performed, one for each analysis. **Safety and effectiveness:** In this follow-up members of all three study cohorts will be followed from the day after start date up until the earliest of: a) first occurrence of Intracranial hemorrhage (intracerebral hemorrhage, subarachnoid hemorrhage, subdural and epidural hematoma), b) an ischemic event (Ischaemic Stroke /Systemic Embolism), c) Myocardial Infarction, d) death, and e) end of study period. **All-cause Mortality:** the follow-up of members of all three study cohorts will be followed from the day after start date up until the earliest of: a) date of death, and b) end of study period. The end of study period is defined as end of last data collection in each practice.

We will then analyze safety, effectiveness, and all-cause mortality associated to use of the study drugs in three independent nested-case control analyses. These three analyses will include all cases identified in each follow-up (respectively: intracranial hemorrhage events, ischemic events, and deaths) and an analysis-specific group of controls. These control groups will comprise a random sample of members of all three cohorts, frequency-matched by age, sex and calendar year to each set of cases ([Walker 1991](#)). Briefly, each cohort member is assigned a random date within the study period. We will consider “eligible controls” all those individuals who are being followed at the time of the random date (e.g. random date included between their start of follow-up and end of follow-up). This process (similar to incidence density sampling) ensures that the likelihood of being selected as control is proportional to the amount of person-time contributed by each patient: as an example a person who contributes all the time included between beginning of study period and end of study period has a 100% likelihood of being an eligible control. Then we will sample “eligible

controls” in such a way that the frequency of matching factors (age categories, sex, and calendar year) among selected controls at their random dates matches that of the cases at the index date (i.e. frequency-matched controls). In other words, if 2% of cases are males, belong to the age category 40-49 and have 2010 as year of their index date, then 2% of controls are males, belong to the age category 40-49 and have 2010 as year of their random date. Under our study design of incidence density sampling, the odds ratio (OR) is an unbiased estimator of the incidence rate ratio (RR) (Rothman 2012). Unconditional logistic regression models will be used to obtain OR estimates of OAC use adjusted by baseline variables described above and OAC use at index date. The model will include all covariates described in section 9.3.3 in the logistic regression model (fully-adjusted model). Additionally, and depending on the number of cases ascertained, we could explore simpler models based on either change-in-estimate or statistical significance approaches. Specifically the following analyses will be performed for each outcome:

- a) OAC daily dose: We will use the daily dose criteria described in 9.3.1.2 to classify current users of rivaroxaban and apixaban and compare with warfarin as follows:

Rivaroxaban

- Overall Rivaroxaban (both doses) vs warfarin
 - o 20mg OD – No dose reduc. criteria – Appropriate vs warfarin
 - o 20mg OD – Dose reduction criteria – Inappropriate vs warfarin
 - o 15mg OD - No dose reduc. criteria – Inappropriate vs warfarin
 - o 15mg OD – Dose reduction criteria – Appropriate vs warfarin
 - o Overall Appropriate use vs warfarin

Apixaban

- o Overall Apixaban (both doses) vs warfarin
 - 5mg Bid - No dose reduc. criteria – Appropriate vs warfarin
 - o 5mg Bid – Dose reduction criteria – Inappropriate vs warfarin
 - o 2.5mg Bid - No dose reduc. criteria – Inappropriate vs warfarin
 - o 2.5mg Bid – Dose reduction criteria – Appropriate vs warfarin
 - o Overall Appropriate use vs warfarin
- b) Outcomes will also be analysed in the sub-group of diabetes and by renal function (CKD-EPI) (creatinine clearance or serum creatinine as described in the label of the respective NOAC). Since renal function is taken into account in this classification, individuals without

renal function values available (expected to be less than 5%) will be excluded from these analyses. Using warfarin current use as the reference category, we will estimate the risk of the study outcomes associated to the rivaroxaban and apixaban daily dose categories described above.

- c) OAC duration: We will use the duration variable described in section 9.3.3. to compare different drug durations of current use with non-use of each study drug. Additionally we will compare “Continuers” and “Discontinuers/Switchers” with non-use of each study drug.
- d) Stratified analysis: The above described analyses will also be conducted separately for naïve, and non-naïve patients at start date.

Comparisons will be done based on adjusted point estimates and confidence intervals obtained from multivariable regression.

We will describe the patterns of use of study medication or other NOACs (edoxaban/dabigatran) after intracranial hemorrhage events, and ischemic events that occurred during the study period. The current hypothesis is that a patient will restart with anticoagulation within 1-3 months of an event.

Strategy for handling missing data

As a general strategy, no data imputation strategies will be applied to supplement missing data. However, missing values may occur in a small proportion. In this case, individuals with missing values will be kept in the analysis and a separate category will be created for missing values of that variable.

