Data analysis	
Describe the three study cohorts i.e. patients prescribed with rivaroxaban, apixaban, warfarin by baseline characteristics, use of medications, comorbidities and healthcare utilization among the three study cohorts and contrast them with the baseline characteristics of patients in relevant, phase III clinical trials.
 
Two independent follow-ups will be performed, one for each analysis. Safety and Effectiveness: In this follow-up members of all three study cohorts will be followed from the day after start date up until the earliest of: a) first occurrence of Intracranial hemorrhage (intracerebral hemorrhage, subarachnoid hemorrhage, subdural and epidural hematoma), b) an ischemic event (Ischaemic Stroke /Systemic Embolism), c) Myocardial Infarction, d) death, and e) end of study period.
 
All-cause mortality: the follow-up of members of all three study cohorts will be followed from the day after start date up until the earliest of: a) date of death, and b) end of study period. The end of study period is defined as end of last data collection

	
in each practice.
 
Analyze safety, effectiveness, and all-cause mortality associated to use of the study drugs in three independent nested-case control analyses. Estimates for standard as well as for reduced dose of study drugs will be obtained. These three analyses will include all cases identified in each follow-up (respectively: intracranial hemorrhage events, ischemic events, and deaths) and an analysis-specific group of controls. These control groups will comprise a random sample of members of all three cohorts, frequency-matched by age, sex and calendar year to each set of cases. Under our study design of incidence density sampling, the odds ratio (OR) is an unbiased estimator of the incidence rate ratio (RR). Unconditional logistic regression models will be used to obtain OR estimates adjusted by baseline variables described above and OAC use at index date.
 
Outcomes will be analysed for the sub-group of NOAC users appropriately and inappropriately receiving standard and reduced dose. Outcomes will be analysed in the sub-group of diabetics and by renal function (CKD-EPI).
 
Further, the patterns of use of study medication before and after intracranial hemorrhage events, and ischemic events that occurred during the study period will be described.

Milestones	The project is planned to begin in December 2018 and will end in December 2019

5. Amendments

None

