9.2.3 Selection criteria

Inclusion criteria

- Patients aged ≥ 18 years of age
- NVAf
- New users of Rivaroxaban, Apixaban, Warfarin
- At least one year enrollment with the general practice (GP)
- One year since first health contact recorded in THIN prior to the first prescription of a study drug

Exclusion criteria

- Patients with other recent indications of OAC initiation as described in section 9.1.
- Individuals on more than one OAC on the start date.
- Users of Rivaroxaban apart from 15/20mg daily dose
- Users of Apixaban apart from 5/10mg daily dose

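### Neither follow-up ends when a patient leaves the practice, so control dates can fall in time that cannot yield a case; this biases the non-use comparisons in Section 9.7(c)

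*Protocol*

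**What the plan says.** The protocol defines two follow-ups (Section 9.7, repeated in the abstract). The safety and effectiveness follow-up runs from the day after the start date to the first of intracranial haemorrhage, an ischaemic event, "c) Myocardial Infarction, d) death, and e) end of study period". The mortality follow-up runs "up until the earliest of: a) date of death, and b) end of study period". In both, the administrative end is a practice date: "The end of study period is defined as end of last data collection in each practice". A year's enrolment is required before entry (Sections 9.1 and 9.2.3), but no rule requires the patient still to be registered later.

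For controls, "each cohort member is assigned a random date within the study period", and a person is eligible when followed on that date, for example "random date included between their start of follow-up and end of follow-up". Section 9.7 then asserts that selection is proportional to the person-time each patient contributes, and that the odds ratio estimates the rate ratio without bias.

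Section 9.3.3 classes use at the index date by time since supply ended: current (up to 30 days), recent (to 90), past (91 to 365) and non-use (none in the prior year). Analyses (a) and (b) of Section 9.7 take current warfarin use as the reference. Analysis (c) is to "compare different drug durations of current use with non-use of each study drug", and also sets Continuers and Discontinuers/Switchers against non-use.

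**The concern.** Density sampling works only if cases and controls come from the same person-time. Section 9.4 describes THIN as what the primary care physician provides, receives and enters. It does not say outright that records stop when a patient leaves, but that follows naturally from the description. A patient who moves away before the practice's last collection then has no further recorded prescriptions, events or death. Under the written rule that patient is still followed and can be drawn as a control, yet cannot become a case.

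The excess control dates are not spread evenly over exposure categories. With no prescriptions visible, they pass quickly out of current use and, after a year, into non-use. Non-use is over-represented among controls only, and any comparison of current use with non-use moves upward. Analysis (c) is run for each outcome and repeated for naïve and non-naïve patients, so the problem recurs there.

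**Working it through.** **Inputs from the protocol.** Study period January 2012 to December 2017, about 6 years (Section 9.2.2). At least 10,000 initiators of each of three drugs, with annual rates of 1%, 2% and 4% for intracranial haemorrhage, ischaemic stroke and death (Section 9.5). Recency windows from Section 9.3.3.

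**Assumptions, not in the protocol.** Leaving rate t of 2% to 8% a year, uniform entry over the 6 years, and the drug-stopping patterns stated below. Matching and covariate adjustment are not modelled.

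**Step 1: the protocol's own figure.** Section 9.5 expects 900, 1,800 and 3,600 events. 30,000 × 0.01 × 3 = 900, 30,000 × 0.02 × 3 = 1,800 and 30,000 × 0.04 × 3 = 3,600. The figures reproduce with a mean follow-up of 3 years, which is implied but not stated.

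**Step 2: share of control time after departure.** Let a = 0.07 + t, where 0.07 = 0.01 + 0.02 + 0.04. Per patient:

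- observed years O = (1/a)[1 − (1 − e^(−6a))/(6a)]
- unobserved years U = (t/a)(3 − O), since a departed patient stays followed to the end of the window
- share s = U/(O + U)

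| t | O | U | s |
|---|---|---|---|
| 2% | 2.53 | 0.11 | 0.040 |
| 5% | 2.39 | 0.25 | 0.096 |
| 8% | 2.27 | 0.39 | 0.146 |

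**Step 3: how that time is coded.** A simulation (2 million patients per scenario, drug stopping 25% a year, death 4% a year, 14 days of remaining supply) codes the dates after departure as about 4% current, 5% recent, 23% past and 68% non-use. So 5 + 23 + 68 = 96% is not current use.

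**Step 4: spurious odds ratio when the truth is 1.** Cases arise only from observed time, so the spurious OR is (current ÷ non-use in observed time) ÷ (current ÷ non-use in eligible control time).

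*Non-use of one drug, with users of the other two counted as non-users* (closest to the wording of 9.7(c)). Take N = 0.62 of observed control time as non-use of rivaroxaban. After departure, count the two-thirds who started another drug, plus f = 0.56 of the remaining third (time more than 1.1 years after departure). No time after departure is counted as current. The inflation is 1 + s(2/3 + f/3)/[N(1 − s)], with 2/3 + 0.56/3 = 0.853. N and f are assumptions of this calculation.

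- t = 2%: 1 + 0.040 × 0.853/(0.62 × 0.960) = 1.06
- t = 5%: 1 + 0.096 × 0.853/(0.62 × 0.904) = 1.15
- t = 8%: 1 + 0.146 × 0.853/(0.62 × 0.854) = 1.24

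*Non-use of a patient's own starting drug, no switching* (the Step 3 simulation):

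| t | Observed: current, non-use | Eligible control time: current, non-use | Spurious OR |
|---|---|---|---|
| 2% | 0.678, 0.196 | 0.653, 0.215 | 1.14 |
| 4% | 0.685, 0.190 | 0.635, 0.227 | 1.29 |
| 6% | 0.690, 0.185 | 0.617, 0.240 | 1.45 |
| 8% | 0.695, 0.180 | 0.600, 0.252 | 1.62 |

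For example, at 8%: (0.695/0.180) ÷ (0.600/0.252) = 3.86 ÷ 2.38 = 1.62. The shares of control dates after departure in this simulation are 4%, 8%, 11% and 15%. Ending follow-up at departure makes the two time bases identical and returns the OR to 1.00.

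**Step 5: contrast with current warfarin.** The observed share of eligible control time coded as current is 0.9976 at 2% leaving and 0.9908 at 8%. Even if users of one drug left at 8% and users of the other at 2%, the distortion is 0.9908/0.9976 = 0.993.

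**The case against.** The main counter-argument is that this leaves the study's main results almost untouched. The primary objectives and the mortality objective compare with warfarin, analyses (a) and (b) use current warfarin as reference, and Step 5 shows a shift of under 1%. No objective or endpoint names the duration comparison. That stands, and it limits the seriousness of the point. A reader might infer that the primary or mortality comparisons with warfarin are compromised, or that person-time rates will be wrong. The document does not support this: the warfarin contrasts hardly move, and the ENCePP checklist marks measures of occurrence as not applicable (item 3.3).

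The size also rests on assumptions. A reader might take "approximately one-third are active at any one time" (Section 9.4) as a leaving rate. It counts everyone ever represented in the database and says nothing about departure among anticoagulated patients in 2012 to 2017. Nor is all time after departure coded non-use, since under Section 9.3.3 that needs a full year without use. A factor of up to 2.0 can be produced for non-use of any anticoagulant at an assumed 10% prevalence, but 9.7(c) specifies non-use of each study drug.

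The planned model adjusts for healthcare utilisation in the prior year, which would partly flag departed controls. With assumed visit distributions and a separate zero-visit category, a spurious OR of 1.38 at 5% leaving falls to 1.21–1.30, and one of about 1.65 at 8% falls to 1.29–1.47. That attenuates the bias without removing it.

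Finally, the reference to contributed person-time suggests that the authors meant observable time. Probably so, but the stated list of censoring events does not deliver it.

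**Conclusion.** The point holds as an error in a stated rule. As written, both follow-ups admit control dates from time in which no case can be recorded, contrary to the property that Section 9.7 claims for the design. At an assumed leaving rate of 2% to 8% a year, about 4% to 15% of control dates are affected. The unadjusted OR for current use against non-use is inflated 1.06- to 1.24-fold when users of the other drugs count as non-users, and 1.14- to 1.62-fold for a patient's own starting drug. For scale, Section 9.5 aims to detect odds ratios of 1.5, 1.3 and 1.2 for current use. The direction does not depend on the assumptions, but the size does. The conclusion rests on the inference that THIN records end at departure. The damage is confined mainly to 9.7(c), so this should be fixed but does not undermine the primary comparisons. It also gives no ground for replacing non-use with current warfarin in 9.7(c). That is a separate question, and the change could not work for warfarin itself, which would become its own reference.

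**What to change.** In Section 9.7 and the abstract, add the date the patient leaves the practice (transfer out or deregistration) to the list of ends for both follow-ups. State that this date is also the upper limit for an eligible control date. Leave the reference category in 9.7(c) as it is.

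The cost is two lines of text and one registration date in the extraction. It should be done before sampling, because every control set depends on it. Person-years fall by the unobserved part (0.11 to 0.39 years per patient in Step 2), but no recordable case is lost. If the implied 3 years in Section 9.5 is administrative follow-up, mean observed time becomes (1 − e^(−3t))/t: 2.91 years at 2% and 2.67 at 8%. Expected events would then be about 873 to 800, 1,747 to 1,600 and 3,494 to 3,201. That shortfall arises from departures themselves, whether or not the text is changed.
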